## 10.6 CONCOMITANT MEDICATIONS

A concomitant medication is defined as any prescription or over-the-counter preparation, including vitamins and supplements. All concomitant medications from 30 days before Day 1 until 30 days after the subject's last dose of study drug or before start of subsequent anticancer treatment (whichever occurs first) must be recorded on the electronic case report form (eCRF). Blood or blood products are not considered concomitant medications and must be recorded on the appropriate eCRF.

### 10.6.1 REQUIRED CONCOMITANT MEDICATIONS

#### 10.6.1.1 Contraception

Females of reproductive potential must commit either to abstain continuously from heterosexual sexual intercourse or to use 2 methods of effective contraception simultaneously (1 highly effective form of contraception—tubal ligation, intrauterine device [IUD], hormonal [birth control pills, injections, hormonal patches, vaginal rings or implants] or partner's vasectomy and 1 additional effective contraceptive method—male latex or synthetic condom, diaphragm, or cervical cap). Contraception must begin 4 weeks prior to initiating treatment and continue during therapy, dose interruptions, and for 28 days after discontinuation of therapy. Reliable contraception is indicated even where there has been

Approved

CONFIDENTIAL

a history of infertility, unless this is due to hysterectomy. Females of reproductive potential should be referred to a qualified provider of contraceptive methods, if needed. Additional details are provided in Pomalidomide Risks of Fetal Exposure, Pregnancy Testing Guidelines and Acceptable Birth Control Methods ([Appendix J](#)), Pomalidomide Education and Counseling Guidance Document ([Appendix K](#)), and Pomalidomide Information Sheet for Subjects Enrolled in Clinical Research Studies ([Appendix L](#)).

Females of reproductive potential must have 2 negative pregnancy tests before initiating study treatment. The first test should be performed within 10–14 days of study treatment and the second test should be performed within 24 hours before study treatment. Once treatment has started and during dose interruptions, pregnancy testing for female subjects of reproductive potential should occur weekly during the first 4 weeks of treatment. Pregnancy testing should be repeated every 4 weeks thereafter for female subjects with regular menstrual cycles. For female subjects with irregular menstrual cycles ( $\pm 7$  days of a 28-day cycle), pregnancy testing should be performed every 2 weeks. Pregnancy testing and counseling should be performed if a subject misses her period or if there is any abnormality in her menstrual bleeding. Study treatment must be discontinued during this evaluation.

Postmenopausal females ( $> 45$  years old and without menses for  $> 2$  years) and surgically sterilized females are exempt.

Male subjects must use an effective barrier method of contraception during the study and for 3 months following the last dose if sexually active with a female of childbearing potential.

Because pomalidomide is present in the semen of male subjects who receive it, they must always use a latex or synthetic condom during any sexual contact with females of reproductive potential and for up to 3 months after discontinuation of study treatment, even if they have undergone a successful vasectomy. Male subjects must agree not to donate sperm while being treated and for up to 3 months after discontinuing treatment.

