**Contraception**

Females of childbearing potential enrolled in this protocol must agree to use 2 reliable forms of contraception simultaneously or to practice complete abstinence from heterosexual intercourse during the following time periods related to this study: 1) for at least 28 days before starting study drug; 2) while participating in the study; 3) dose interruptions; and 4) for at least 28 days after study treatment discontinuation.

The 2 methods of reliable contraception must include 1 highly effective method and 1 additional effective (barrier) method. An FCBP must be referred to a qualified provider of contraceptive methods if needed.

Approved

The following are examples of highly effective and additional effective methods of contraception:

- Highly effective methods:
  - Intrauterine device (IUD)
  - Hormonal (birth control pills, injections, implants)
  - Tubal ligation
  - Partner's vasectomy
- Additional effective methods:
  - Male condom
  - Diaphragm
  - Cervical cap

Because of the increased risk of venous thromboembolism in patients with multiple myeloma taking pomalidomide and dexamethasone, combined oral contraceptive pills are not recommended. If a subject is currently using combined oral contraception the subject should switch to another one of the effective methods listed above. The risk of venous thromboembolism continues for 4–6 weeks after discontinuing combined oral contraception.

The efficacy of contraceptive steroids may be reduced during co-treatment with dexamethasone.

Implants and levonorgestrel-releasing intrauterine systems are associated with an increased risk of infection at the time of insertion and irregular vaginal bleeding. Prophylactic antibiotics should be considered, particularly in subjects with neutropenia.

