**To be completed prior to each dispensing of pomalidomide**

**Do Not Dispense pomalidomide if:**

- The patient is pregnant.
- No pregnancy tests were conducted for a FCBP.
- The patient states she did not use TWO reliable methods of birth control (unless practicing complete abstinence of heterosexual intercourse) [at least 28 days prior while taking pomalidomide, during dose interruption, and 28 days after discontinuation of pomalidomide].

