**FCBP**

**1. I verified that the required pregnancy tests performed are negative.**

**2. I counseled FCBP regarding the following:**

- Potential fetal harm: If pomalidomide is taken during pregnancy, it may cause birth defects or death to any unborn baby. Females are advised to avoid pregnancy while taking pomalidomide. The teratogenic potential of pomalidomide in humans cannot be ruled out. Females of childbearing potential must agree not to become pregnant while taking pomalidomide.

Approved

CONFIDENTIAL

- Using TWO reliable methods of birth control at the same time or complete abstinence from heterosexual intercourse [at least 28 days prior, while taking pomalidomide, during dose interruption, and 28 days after discontinuation of pomalidomide].
- Continuation of TWO reliable methods of birth control or complete abstinence if therapy is interrupted.
- That even if she has amenorrhea she must comply with advice on contraception.
- Use of one highly effective method and one additional method of birth control AT THE SAME TIME. The following are examples of highly effective and additional effective methods of contraception:
  - Highly effective methods:
    - Intrauterine device (IUD)
    - Hormonal (birth control pills, injections, implants)
    - Tubal ligation
    - Partner’s vasectomy
  - Additional effective methods:
    - Male condom
    - Diaphragm
    - Cervical cap
- Pregnancy tests before and during treatment, even if the patient agrees not to have reproductive heterosexual intercourse. Two pregnancy tests will be performed prior to receiving study drug, one within 10–14 days and the second within 24 hours of the start of pomalidomide.
- Frequency of pregnancy tests to be done:
  - Every week during the first 28 days of this study and a pregnancy test every 28 days during the patient’s participation in this study if menstrual cycles are regular or every 14 days if cycles are irregular.
  - If the patient missed a period or has unusual menstrual bleeding.
  - When the patient is discontinued from the study and at Day 28 after study drug discontinuation if menstrual cycles are regular. If menstrual cycles are irregular, pregnancy tests will be done at discontinuation from the study and at Days 14 and 28 after study drug discontinuation.
- Stop taking pomalidomide immediately in the event of becoming pregnant and to call their study doctor as soon as possible.
- NEVER share pomalidomide with anyone else.

Approved

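### Section 10.6.1.1 and the Appendix J dispensing script list birth control pills with no caution, while Appendix I advises against combined pills and warns that dexamethasone may weaken steroid contraceptives

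*Protocol*

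**What the plan says.** Three places in the protocol tell a site which contraceptive methods count.

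- **Section 10.6.1.1** requires continuous abstinence or two methods used together, one highly effective and one additional. Among the highly effective forms it includes "hormonal [birth control pills, injections, hormonal patches, vaginal rings or implants". It does not separate combined pills from other pills, and it mentions neither clot risk nor dexamethasone. For further detail it cites three appendices by title and letter, the first of them as "Acceptable Birth Control Methods ([Appendix J".
- **Appendix I** (fetal risk, pregnancy testing and birth control) also lists birth control pills as highly effective. It then adds that, given the raised clot risk in patients with "multiple myeloma taking pomalidomide and dexamethasone, combined oral contraceptive pills are not recommended". The next sentence reads "If a subject is currently using combined oral contraception the subject should switch to another one of the effective methods listed above". A separate sentence reads "The efficacy of contraceptive steroids may be reduced during co-treatment with dexamethasone".
- **Appendix J** (education and counselling guidance) is marked "To be completed prior to each dispensing of pomalidomide". Its highly effective methods include "Hormonal (birth control pills, injections, implants". The script as supplied carries none of the Appendix I cautions.

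Section 10.3 plans dexamethasone for all subjects on eight days of each 28-day cycle. The Appendix I cautions that depend on dexamethasone therefore bear on every woman of childbearing potential in the study.

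**The concern.** The cautions appear in only one of the three places, and not in the two that a site is most likely to work from: the body of the protocol, and the script gone through at each dispensing. A woman on a combined pill who also uses a condom satisfies 10.6.1.1. She also passes the Appendix J do-not-dispense check, which asks about pregnancy, pregnancy testing and whether two reliable methods were used. Under Appendix I the same woman should be moved to another method.

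What is at stake is subject safety and consistent conduct across about 35 sites. Appendix I describes pomalidomide as teratogenic in rabbits and as an analogue of a known human teratogen. The protocol also treats thrombosis as a real hazard: Section 10.6.1.6 requires prophylaxis, and exclusion criterion 10 excludes patients who cannot take it.

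**Working it through.** The protocol states no figure on this point, so there is nothing to recompute. The check is a comparison of the three texts.

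| Item | 10.6.1.1 | Appendix I | Appendix J |
|---|---|---|---|
| Birth control pills listed as highly effective | yes | yes | yes |
| Second method required unless abstinent | yes | yes | yes |
| Methods introduced as examples | no | yes | yes |
| Patches and vaginal rings named | yes | no | no |
| Combined pills advised against | no | yes | no |
| Current users told to switch | no | yes | no |
| Warning on dexamethasone and contraceptive steroids | no | yes | no |

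1. The first two rows agree. All three texts name pills, and all three require a second method.
2. The last three rows differ. Each caution stands in Appendix I alone.
3. Appendix I is also unclear within itself. A combined-pill user is told to move to a method listed above, and that list still contains birth control pills with no type specified. The likely intent is pills other than combined ones, or a non-hormonal method, but the text does not say.
4. The cross-reference in 10.6.1.1 names the right appendix by title but gives the letter J. In the current contents list that title belongs to Appendix I, and J is the counselling script. The other two letters in the sentence are off by one in the same way: the counselling document is cited as K but is J, and the information sheet is cited as L but is K. A reader who follows the title finds the cautions. A reader who follows the letter does not.
5. Appendix J tells the counsellor to hand over the Pomalidomide Information Sheet (Appendix K). That sheet was not in the text available, so it is unknown whether it carries the cautions. If it does, the patient would see them, but 10.6.1.1 and the counselling script would still lack them.

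**The case against.** The best case on the other side is that this is ordinary layering: a general list in the body, with narrower advice in the appendix that the body cites by its full title. Much of that stands.

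- Appendix I advises; it does not prohibit. Its advice on pills covers combined pills only, and its dexamethasone sentence restricts no method. The texts therefore differ in what they caution, and no page forbids what another allows.
- A reader might infer that pills are accepted without any limit. They are not: a second, barrier-type method is required on every page.
- A reader might infer that patches and rings are in conflict because only 10.6.1.1 names them. Appendices I and J offer their lists as examples, so absence from them is not exclusion.
- A reader might infer that the wrong letter misdirected sites. The protocol's opening note says that Amendment 3 was never implemented. The Amendment 2 summary of changes places the neuropathy tool at M and the pain inventory at N, and the current contents list has them at L and M. The same one-letter shift, after the deletion of Appendices C1 and C2, would have made J correct under Amendment 2. The ECOG reference in Section 6.1 shows the same slip, so this is a clerical fault across the document.
- A reader might infer a threat to dose-limiting toxicity (DLT) calls, or use the period of 4 to 6 weeks for which Appendix I says clot risk persists to measure the problem. Neither is supported. That period concerns a woman who has already stopped the combined pill, so it would remain after the texts are aligned. Section 10.5 already weighs concomitant medication in judging relatedness, Section 10.6 records such medication from 30 days before Day 1, and Section 5.1.3 has the Cohort Safety Review Committee discuss each subject. Nothing shows that the wording difference would change a call.

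What the objection does not remove is that the script used at every dispensing omits advice that the protocol itself gives, and that 10.6.1.1 omits it too.

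**Conclusion.** The point holds as an inconsistency in safety wording that should be corrected. Section 10.6.1.1 and Appendix J present birth control pills with no caution. Appendix I advises against combined pills, tells users to switch and warns about contraceptive steroids with dexamethasone.

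Its size cannot be computed. The number of women of childbearing potential among the roughly 82 planned subjects is not stated, and that it is small is an assumption. SAP Section 7.3.1 tabulates baseline fertility status, so the number could be reported. No endpoint, estimate, sample size or escalation rule depends on the point.

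The conclusion rests on the protocol text supplied, which is Amendment 3. Its summary of significant changes records no edit to these method lists, so the same difference presumably stood in the active Amendment 2; that is an inference. The conclusion also assumes that sites use 10.6.1.1 and Appendix J as written, and it leaves open what the patient information sheet says.

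**What to change.** Reconcile three texts: Section 10.6.1.1, the method lists in Appendices I and J, and the Appendix I cautions on combined pills and on dexamethasone. The same list and the same cautions should then appear in all three. Within Appendix I, make clear which listed methods a combined-pill user may move to. Correct the three appendix letters in 10.6.1.1, and check that the patient information sheet agrees. Which methods are acceptable, and how strong each caution should be, is for the sponsor's clinical team.

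The cost is protocol wording and a revised counselling script. No visits, tests or subjects are added, and the SAP does not change.

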#### **10.6.1.2 Antinausea and Antiemetics**

It is strongly recommended that subjects be premedicated with a 5-HT3 inhibitor, such as ondansetron or granisetron, prior to administration of the first dose of oprozomib each day

Approved

and throughout the day as needed to prevent nausea and vomiting. If nausea/vomiting at any grade persists, aprepitant or fosaprepitant is recommended. Additional antiemetics may be used per investigator discretion.

#### **10.6.1.3 Antidiarrheals**

For subjects developing any grade of diarrhea, loperamide (Imodium) is strongly recommended at the first onset of symptoms. For subjects with persistent diarrhea despite the use of Imodium, the use of diphenoxyllate/atropine (Lomotil) is strongly recommended. Other antidiarrheal agents may be used if necessary; a work-up for other etiologies is suggested if diarrhea continues despite the prior 2 agents.

#### **10.6.1.4 Antivirals**

Valacyclovir or an equivalent antiviral is recommended for the duration of treatment to prevent Herpes zoster (additional prophylaxis is at the investigator's discretion).

#### **10.6.1.5 Acid-related Medications**

Lansoprazole or another oral proton-pump inhibitor is required (unless subject has intolerance or hypersensitivity) for the duration of treatment to prevent peptic disease or other GI toxicities.

#### **10.6.1.6 Thrombo-prophylaxis**

Aspirin (or other anticoagulant or antiplatelet medication such as clopidogrel bisulfate, low-molecular-weight heparin, or warfarin based on subject risk factors for deep vein thrombosis) while taking pomalidomide is required to prevent thrombosis (refer to the Pomalidomide Prescribing Information [[Celgene Corporation, 2013](#)] for more information).

#### **10.6.1.7 Tumor Lysis Syndrome**

Monitoring and Prophylaxis Guidelines: Oral hydration of 1.5–2 liters per 24 hours must be instituted in all subjects 24–48 hours prior to initiation of therapy for every cycle and continued throughout every day of oprozomib dosing. Premedication with allopurinol or other approved uric acid-lowering agents is highly recommended for subjects with high tumor burden (i.e., for multiple myeloma: Durie-Salmon or International Staging System

Approved

Stage II/III, or rapidly increasing M-protein or light chains) or compromised renal function (CrCl < 50 cc/min). These subjects may be at elevated risk for TLS and should be closely monitored. Uric acid levels should be normalized prior to initiation of treatment, if appropriate.

#### **Tumor Lysis Syndrome Laboratory Abnormalities**

Subjects with laboratory abnormalities prior to dosing that are consistent with lysis of tumor cells (e.g., as defined by abnormalities in at least 3 of the following 4 categories: [1] a 2-fold increase of lactate dehydrogenase above the ULN; [2] increases in serum creatinine, uric acid, or phosphorus > 50% over baseline; [3] potassium increases > 30% above the ULN; or [4] calcium decreases from baseline of > 20% in the absence of concomitant bisphosphonate therapy) (Sezer, 2006). Subjects must not receive the scheduled dose prior to institution of the aforementioned preventive measures.

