**Table 13 Guidelines for Dose Modification of Oprozomib/Placebo and Pomalidomide for Hematologic Toxicities**

Findings	Oprozomib	Pomalidomide
Findings on Day 1 of Cycle		
Recommended Action		
Platelets $< 25 \times 10^9/L$	Hold dose a until recovery $\geq 25 \times 10^9/L$ ; restart at previous dose.	Not applicable.
Platelets $< 30 \times 10^9/L$	Not Applicable.	Hold dose a , follow CBCs. Hold prophylactic anticoagulation until platelets return to $\geq 30 \times 10^9/L^a$ , then resume at 1 dose decrement.
ANC $< 0.5 \times 10^9/L$ or febrile neutropenia (fever $\geq 38.5^\circ C$ and ANC $< 1.0 \times 10^9/L$ )	Hold dose a . Add colony stimulating factor b With resolution to $\geq 1.0 \times 10^9/L$ , restart at previous dose.	Hold dose a . Add colony stimulating factor b With resolution to $\geq 0.5 \times 10^9/L$ , restart at 1 dose decrement.
Findings on Subsequent Days of Cycle		
Recommended Action		
Platelets 25 to $< 50 \times 10^9/L$ without $\geq$ Grade 2 bleeding/hemorrhage	Full dose.	Full dose.
Platelets 25 to $< 50 \times 10^9/L$ with $\geq$ Grade 2 bleeding/hemorrhage	Hold dose a until platelets return to $\geq 50 \times 10^9/L$ and/or bleeding is controlled, then resume at 1 dose decrement.	Hold dose a until platelets return to $\geq 50 \times 10^9/L$ and/or bleeding is controlled, then resume at 1 dose decrement.
Platelets $< 25 \times 10^9/L$ or thrombocytopenia with $\geq$ Grade 2 bleeding/hemorrhage	Hold dose a until recovery to $\geq 25 \times 10^9/L$ ; restart at 1 dose decrement.	Hold dose a . Hold prophylactic anticoagulation until platelets return to $\geq 30 \times 10^9/L^a$ , then resume at 1 dose decrement.
Neutropenic fever (ANC $< 1.0 \times 10^9/L$ and single temperature $> 38.3^\circ C$ or temperature $> 38.0^\circ C$ sustained for more than 1 hour)	Hold dose a ; follow CBC at least 3 times per week. Add colony stimulating factor b With resolution of fever and ANC $\geq 1.0 \times 10^9/L$ , restart at 1 dose decrement.	Hold dose a ; follow CBCs. Add colony stimulating factor b . With resolution of fever and ANC $\geq 1.0 \times 10^9/L$ , restart at 1 dose decrement.

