**Table 14 Guidelines for Dose Modification of Oprozomib/Placebo and Pomalidomide for Nonhematologic Toxicities**

Symptom	Findings	Recommended Action a	
		Oprozomib	Pomalidomide
Tumor Lysis Syndrome	Generally recognized in at least 3 or more of the following categories: (1) Increase in creatinine, uric acid, or phosphate of $\geq 50\%$ (2) Increase in potassium of $\geq 30\%$ (3) Decrease in calcium of $\geq 20\%$ , or (4) Increase in LDH $\geq 2$ -fold from baseline	Hold both oprozomib and pomalidomide until all abnormalities in serum chemistries have resolved to baseline; resume at full doses.	
Neuropathy	Grade 2 neuropathy with pain or $\geq$ Grade 3 neuropathy	Hold dose until toxicity resolves to $\leq$ Grade 1 or has returned to baseline. Resume study drug at 1 dose decrement.	Hold dose until toxicity resolves to $\leq$ Grade 1 or has returned to baseline. Resume study drug at 1 dose decrement from previous dose.
Infection	Grade 3 or 4	Hold both oprozomib and pomalidomide until systemic treatment for infection complete. If ANC $\geq 1.0 \times 10^9/L$ , resume both drugs at full dose. If ANC $< 1.0 \times 10^9/L$ , follow hematologic toxicities dose reduction guidelines (Table 13).	
Nausea, vomiting, diarrhea, or constipation	$\geq$ Grade 3 without optimal supportive care as defined by use of both a 5-HT 3 antagonist and aprepitant	Oprozomib-related: Full dose oprozomib but institute optimal supportive care.	Pomalidomide-related: Hold dose until toxicity resolves to $\leq$ Grade 1 or has returned to baseline. Resume study drug at 1 dose decrement from previous dose.
	$\geq$ Grade 3 with optimal supportive care as defined by use of both a 5-HT 3 antagonist and aprepitant	Oprozomib-related: Hold dose until toxicity resolves to $\leq$ Grade 1 or has returned to baseline. Resume study drug at 1 dose decrement.	
Fatigue	Grade 3 fatigue lasting $< 14$ days	Full dose.	Hold dose until toxicity resolves to $\leq$ Grade 1 or has returned to baseline. Resume study drug at 1 dose decrement from previous dose.
	Grade 3 fatigue lasting $\geq 14$ days	Hold dose until toxicity resolves to $\leq$ Grade 1 or has returned to baseline. Resume study drug at 1 dose decrement.	

Approved

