#### **Tumor Lysis Syndrome Treatment Guidelines**

If TLS occurs as defined by the laboratory abnormalities described above, cardiac rhythm, fluid, and serial laboratory monitoring should be instituted. Correction of electrolyte abnormalities, monitoring of renal function and fluid balance, and administration of therapeutic and supportive care, including dialysis, should be done as clinically indicated. In the setting of TLS, oprozomib treatment will be interrupted until resolution of all clinical and laboratory abnormalities consistent with TLS. Once TLS has resolved, the subject can resume treatment at the initial dose level. The **Sponsor's** study medical monitor should be consulted if there is a treatment delay > 4 weeks.

All cases of TLS must be reported to **the Sponsor** as an SAE as outlined in [Section 13.5](#).

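### Tumor lysis syndrome is defined two ways in the protocol, so dose holds and SAE reporting can depend on which section a site follows

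*Protocol*

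**What the plan says.** TLS appears in two places in the protocol.

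- **Table 14 (Section 10.4.2.1.2).** TLS is described as "Generally recognized in at least 3 or more of the following categories". The four are: creatinine, uric acid or phosphate up at least 50%; potassium up at least 30%; calcium down at least 20%; and LDH at least 2-fold from baseline. The action is "Hold both oprozomib and pomalidomide until all abnormalities in serum chemistries have resolved to baseline; resume at full doses".
- **Section 10.6.1.7.** The laboratory list also asks for 3 of 4 categories: "a 2-fold increase of lactate dehydrogenase above the ULN"; creatinine, uric acid or phosphorus more than 50% over baseline; potassium more than 30% above the ULN; and calcium down more than 20% from baseline without concomitant bisphosphonate. The treatment guidelines that follow adopt this list as the definition of TLS and state: "In the setting of TLS, oprozomib treatment will be interrupted until resolution of all clinical and laboratory abnormalities consistent with TLS". They also require every TLS case to be reported as an SAE.

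Section 10.6.2 allows bisphosphonates during the study.

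Febrile neutropenia is worded three times, always with ANC below 1.0 × 10⁹/L:

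- Table 13, Day 1 of a cycle: fever of at least 38.5 °C.
- Table 13, subsequent days: a single reading above 38.3 °C, or above 38.0 °C for more than 1 hour.
- DLT definition (Section 10.5, with the same thresholds in the synopsis): at least 38.3 °C once, or at least 38.0 °C for over 1 hour.

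**The concern.** TLS triggers both a treatment interruption and mandatory SAE reporting. If two sites apply different lists to the same laboratory results, one holds drug and files an SAE while the other does neither. The SAP (Section 7.6.1) summarizes and lists serious adverse events, so the difference would reach the study report. A hold in Cycle 1 that is not a DLT also goes to the Cohort Safety Review Committee for a decision on evaluability (Section 10.5).

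The event is not remote. Section 3.5.1 reports TLS as a DLT at both 240 mg and 270 mg on the 5/14 schedule in the single-agent study.

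**Working it through.** The plan states no figure to reproduce. The check sets the two TLS lists side by side and applies each to the same hypothetical subjects.

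| Category | Table 14 | Section 10.6.1.7 |
|---|---|---|
| Creatinine, uric acid or phosphate | up ≥ 50% | > 50% over baseline |
| Potassium | up ≥ 30%, no ULN reference | > 30% above ULN |
| Calcium | down ≥ 20%, no exception | down > 20%, not on bisphosphonate |
| LDH | ≥ 2 × baseline | 2-fold above ULN |
| Needed | 3 of 4 | 3 of 4 |
| Drugs named | oprozomib and pomalidomide | oprozomib |

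**Assumptions.** The documents give no ULN values. LDH ULN 250 U/L and potassium ULN 5.0 mmol/L are assumed, and the subjects' values are illustrative. A 2-fold increase above the ULN is read as at least 2 × ULN. Table 14's potassium rise is taken from the subject's own baseline. The Section 10.6.1.7 cut-offs are then 2 × 250 = 500 U/L for LDH and 1.3 × 5.0 = 6.5 mmol/L for potassium.

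**Subject A:** LDH 150 to 320, potassium 3.6 to 4.8, creatinine +60%.
- Table 14: 320/150 = 2.13, met. 4.8/3.6 = 1.33, met. Creatinine met. **3 of 4: TLS.**
- Section 10.6.1.7: 320 < 500, not met. 4.8 < 6.5, not met. Creatinine met. **1 of 4: not TLS.**

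**Subject B:** LDH 400 to 520, potassium 5.2 to 6.6, creatinine +60%.
- Table 14: 520/400 = 1.30, not met. 6.6/5.2 = 1.27, not met. Creatinine met. **1 of 4: not TLS.**
- Section 10.6.1.7: 520 ≥ 500, met. 6.6 > 6.5, met. Creatinine met. **3 of 4: TLS.**

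**Subject C:** LDH 260 to 530, potassium 4.0 to 4.5, calcium −23%, creatinine +60%, on a bisphosphonate.
- Table 14: 530/260 = 2.04, met. Calcium met. Creatinine met. **3 of 4: TLS.**
- Section 10.6.1.7: 530 ≥ 500, met. Creatinine met. Calcium not counted. **2 of 4: not TLS.** Without the bisphosphonate it would be 3 of 4.

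**Sensitivity to the assumptions.**
- Table 14, as read here, uses no ULN, so its counts do not change with the ULNs.
- Subject A becomes TLS under Section 10.6.1.7 only if the LDH ULN is at most 320/2 = 160 and the potassium ULN is also below 4.8/1.3 = 3.69.
- Subject B needs an LDH ULN of at most 520/2 = 260 and a potassium ULN below 6.6/1.3 = 5.08, so this example is the most sensitive.
- Subject C stays below 3 of 4 for any LDH ULN, provided the potassium ULN is not below 4.5/1.3 = 3.46.
- If the LDH criterion means 3 × ULN (750 U/L), A stays at 1 of 4, C falls to 1 of 4 and B falls to 2 of 4. The reverse example would then need a higher LDH.
- If Table 14's potassium rise were measured from the ULN, A would meet 2 of 4 there and no longer illustrate the conflict. B would meet 2 of 4 there and C still 3 of 4, so both would still be classified differently.

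**Febrile neutropenia at ANC 0.8.**

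| Temperature | Table 13, Day 1 | Table 13, later days | DLT |
|---|---|---|---|
| exactly 38.3 °C | no | no | yes |
| 38.4 °C | no | yes | yes |
| sustained at exactly 38.0 °C | no | no | yes |
| sustained at 38.1 °C | no | yes | yes |
| 38.6 °C | yes | yes | yes |

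After Day 1, Table 13 and the DLT definition disagree only at the exact cut-off.

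**The case against.** Both TLS lists are hedged, one as a general description and the other as an example, so they could be read as guidance. Both need 3 of 4 categories, so a single LDH criterion changing does not by itself change the classification. Section 10.6.1.7 does not say that oprozomib alone is interrupted; it says nothing about pomalidomide, and a site can satisfy both passages by holding both drugs. The last argument stands: the action is incomplete in one place rather than opposite. The hedging does not remove the conflict, because the treatment guidelines then use the Section 10.6.1.7 list as the definition. The worked subjects change classification on the full 3-of-4 rule.

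Two stronger readings are tempting.

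- **DLT counts, and so the MTD, depend on the site.** A reader might infer this because TLS was a DLT in the single-agent study. Section 10.5 does not list TLS as a criterion. Nonhematologic DLTs are drug-related toxicities of Grade 3 or higher with stated exceptions, graded by NCI-CTCAE 4.03 and reviewed by the committee (Section 5.1.3). No route from the two laboratory lists to a different DLT count is shown.
- **Febrile neutropenia is held or not depending on the page.** The 38.5 °C and 38.3 °C rows sit in one table under separate cycle-day headings, so only one applies on a given day. A subject at 38.4 °C escapes the Day 1 row only with ANC from 0.5 to below 1.0, because ANC below 0.5 triggers that row at any temperature. The DLT thresholds are the same in the synopsis and Section 10.5.

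**Conclusion.** The TLS definitions conflict in the reference point for LDH, in the ULN reference for potassium and in the bisphosphonate exception for calcium, with small differences between strict and non-strict cut-offs. Neither list contains the other: under the stated assumptions subjects can be TLS by Table 14 alone or by Section 10.6.1.7 alone. The drugs to be held are also stated differently, by omission. Dose holds and SAE counts can therefore vary with the section a site follows.

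How often this would happen cannot be estimated from the documents. The examples rest on assumed ULNs, and the direction shown by Subject B is the most sensitive to them. The bisphosphonate example does not depend on the LDH ULN.

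The febrile-neutropenia point is minor: a mismatch at exactly 38.3 °C or 38.0 °C, and a Day 1 threshold whose intent the documents do not explain.

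**What to change.** Reconcile Table 14 with the laboratory and treatment paragraphs of Section 10.6.1.7, so that the protocol has one TLS definition and one statement of which drugs are held. The sponsor must decide the content; this review takes no view on which criteria or action is right. Align the inequality signs for febrile neutropenia between Table 13 (subsequent days) and the DLT definition in the synopsis and Section 10.5, and have the sponsor confirm that the 38.5 °C Day 1 row is intended as a separate rule.

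The cost is wording in two tables and two sections, with no change to sample size or planned analyses. The protocol's cover note says Amendment 3 was approved but not implemented, so the study report should also state which TLS definition was applied to the reported cases.
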